### **Objectives:**

We aim to compare the relative intubating efficacies of these two boxes. This study assesses the time to successful intubation as the primary outcome. Our secondary outcomes will be the quality of the laryngoscopy view (objectively defined as "percentage of glottic opening" / POGO) and ease of intubation.

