### Methodology:

This is a prospective randomized cross over trial to compare the time for intubation using these two devices by our anaesthetists. The planned duration from planning to recruitment to completion of study will be from 1st May 2020 to 31st December 2020. We will recruit eligible anaesthetists after obtaining written informed consent. The anaesthetist should have more than 5 years of experience with intubation as well as experience with intubating patients using videolaryngoscope for more than 20 times.

The anaesthetist will be randomised to intubate the manikin in either Box A or Box B first. The primary endpoint which is the time to successful intubation (defined as the interval from insertion of the laryngoscope blade into the mouth to inflation of the tracheal tube cuff) will be recorded. Other endpoints are the numbers of intubation attempts (each attempt defined as complete removal of video laryngoscope from mouth and reinsertion) will be recorded. Failed insertion is defined as the entire intubation procedure taking more than 120 seconds or more than 3 insertion attempts.

The participants will evaluate their intubation experience using both boxes with a questionnaire based on the ISO9421-11 standard, that is effectiveness, efficiency and satisfaction.

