### Sample size:

The primary endpoint of the study is time to successful tracheal intubation. Sample size is based on a calculation of 10.0 s as the clinically relevant difference in intubation time, with a prospective power analysis at 80% power and 0.05 level of significance. It shows that a sample of 28 laryngoscopists would be required. This will be a cross over study, hence we will recruit 30 laryngoscopists to also account for dropouts and protocol breaches. In view that the time to successful intubations data are not normally distributed, we will use the Mann Whitney U test to analyse intubation times. Categorical data such as number of intubation attempts will be evaluated for differences among the groups using the chi-square test. All statistical analyses

will be performed using IBM SPSS statistics 23 database. A value of p < 0.05 is considered significant.

[figure not shown]

Figure 1 (Box A). Dimensions are 50 cm by 50 cm (height x width), with a thickness of 40 cm. (Source: https://sites.google.com/view/aerosolbox/design)

[figure not shown]

Figure 2 (Box B). Dimensions are 46 cm x 58 cm (height x width) with a thickness of 51cm. The upper portion of the box facing the intubator is made slanted at a 150 degree angle hence providing better ergonomics to the intubator. The curved design at one end of the box is to accommodate the obese/big build patient whose shoulder breadth may be wider than the box's width.

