# MILESTONES AND DATES CHART PROJECT TITLE: TAIWAN "AEROSOL BOX" VERSUS UMMC "INTUBATION BOX": CLINICAL EVALUATION OF THE "INTUBATION BOX" FOR EASE OF INTUBATION

									YEA	R 202	0							
	Apr	Apr	Ma	May	June	June	Jul	Jul	Aug		Sept	Sept	Oct	Oct	Nov	Nov	Dec	Dec
	1-	16-	у	16-	1-15	16-	1-	16-	1-	16-	1-	16-	1-	16-	1-	16-	1-	16-30
	15	30	1- 15	31		30	15	31	15	31	15	30	15	31	15	30	15	
ACTIVITIES			13															
Submission for ethics committee approval																		
Preparation of resources required																		
Data collection																		
Data entry																		
Data analysis																		
Writing of report																		
Submission of completed paper to ISI journal																		

Part 1: User profile			
Name:			
Professional category:	:		
Anaesthesia experienc	ce:		
Age:			
Gender:			
Part 2: Intubating co	onditions pr	ofile	
For direct laryngoscop	-		
		T-: D	HMMC D
Findings Time for successful		Taiwan Box	UMMC Box
(seconds)	IIIIuoaiioii		
Number of intubatio	n attempts		
POGO grading (%)			
Cormack Lehane gra	ade (1-4)		
For videolaryngoscop	y:		
Findings		Taiwan Box	UMMC Box
Time for successful		Turwun Don	CHAIC BOX
(seconds)			
Number of intubation	n attempts		
POGO grading (%)			
Cormack Lehane gra	ide (1-4)		
Part 3: Usability pro	file		
In this section, we wo		now the usability of this eq	uipment (Taiwan Box vs UMMC Box)
during intubation.			
When using for intul	hation with	direct laryngoscopy:	
Findings	vativn With	Taiwan Box	UMMC Box
On a scale of 0-			
10, how easy was	0	10	0

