**Data collection sheet** 

Findings		Taiwa	n Box		UMMC Box					
On a scale of 0-10, how easy was it to use this box?	0 — Very o	difficult	Very	→ 10 y easy	0 — Very o	difficult	Very easy			
Please choose your level of			]	Degree of	agreement	:				
agreement with the statements below.	1: Strongly disagree	2: Disagree	3: Agree	4: Strongly agree	1: Strongly disagree	2: Disagree	3: Agree	4: Strongly agree		
It is comfortable for me to use										

this equipment				
My visual field is				
clear while using				
this equipment				
My hand				
movements were				
free while using				
this equipment				

[figure not shown]
When using for intubation with videolaryngoscopy:

Findings	Intubutio		n Box	ору .	UMMC Box					
On a scale of 0-10, how easy was it to use this box?	0 — Very	difficult	Very easy		0 Very difficult		Very easy			
Please choose your level of										
agreement with the statements below.	1: Strongly disagree	2: Disagree	3: Agree	4: Strongly agree	1: Strongly disagree	2: Disagree	3: Agree	4: Strongly agree		
It is comfortable for me to use this equipment										
My visual field is clear while using this equipment										
My hand movements were free while using this equipment										

Which box would you prefer to use?
Do you have any suggestions on how we can improve this equipment?

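### Number of attempts is to be compared with a chi-square test for separate groups, although every anaesthetist is recorded in both boxes and the counts are ordered

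*Combined protocol and SAP*

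**What the plan says.** The Methodology section describes the design: "This is a prospective randomized cross over trial to compare the time for intubation using these two devices by our anaesthetists". Only the order of the boxes is randomised: "The anaesthetist will be randomised to intubate the manikin in either Box A or Box B first". Part 2 of the data collection sheet has a Taiwan Box column and a UMMC Box column for the same person, once under "For direct laryngoscop" and again under "For videolaryngoscop". Part 3, the usability questionnaire, follows the same layout.

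For categorical outcomes the Sample size section says: "Categorical data such as number of intubation attempts will be evaluated for differences among the groups using the chi-square test". No McNemar, signed-rank, marginal homogeneity or mixed-model analysis is named anywhere in the plan.

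Number of attempts is listed under other endpoints in Methodology. It is not among the secondary outcomes in Objectives, which are the laryngoscopy view and ease of intubation. Failure has its own definition: "Failed insertion is defined as the entire intubation procedure taking more than 120 seconds or more than 3 insertion attempts".

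**The concern.** A chi-square test on the table of box by number of attempts treats the two rows as different people. Here they are the same people. When a person who needs several attempts in one box tends to need several in the other, the difference between boxes varies less than the test assumes. The p-value is then too large and the true error rate falls below the stated 5%. The test also uses only the marginal counts, so it gives the same answer whichever individuals differed between boxes.

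It also treats one, two and three attempts as unordered labels. That is not invalid, but it wastes information, and with 30 people the upper categories are sparse. A non-significant result on attempts could then be read as the boxes being alike when the test has discarded what the crossover was set up to collect.

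**Working it through.** **Inputs.** From the plan: 30 anaesthetists, each using both boxes; significance at 0.05 (taken as two-sided). The plan gives no attempt rates and no within-person correlation, so these are assumed and varied. The stated requirement of 28 concerns intubation time, comes without a standard deviation, and plays no part here.

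**Step 1: why the level is wrong.** For a yes/no outcome with the same success rate p in both boxes and within-person correlation φ, the variance of the difference in proportions is 2p(1−p)(1−φ)/n. The chi-square test uses 2p(1−p)/n. Its true level is therefore about P(|Z| > 1.96/√(1−φ)). Take p = 0.80 and normal latent scores for each person's two results:

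- Latent correlation 0.3: both succeed with probability 0.666, so φ = (0.666 − 0.64)/0.16 ≈ 0.16 and the level is about 3.2%.
- Latent correlation 0.6: both succeed with probability 0.699, so φ = (0.699 − 0.64)/0.16 ≈ 0.37 and the level is about 1.4%.

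Simulation (40,000 trials of 30 pairs) gives 5.0% / 3.2% / 1.5% at latent correlation 0 / 0.3 / 0.6, in agreement.

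**Step 2: number of attempts.** Same simulation, four ordered categories. The unpaired ordinal test is a tie-corrected Mann-Whitney test, included to separate the effect of order from that of pairing. Entries are rejection rates at latent correlation 0 / 0.3 / 0.6.

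| First-pass rates | Chi-square | Unpaired ordinal | Signed-rank |
|---|---|---|---|
| 80% vs 80% (no difference) | 2.8 / 2.1 / 1.5% | 5.0 / 3.1 / 1.3% | 4.7 / 4.6 / 4.4% |
| 90% vs 90% (no difference) | 2.0 / 1.5 / 1.0% | 5.2 / 3.7 / 1.8% | 3.6 / 3.3 / 2.8% |
| 65% vs 90% | 44 / 44 / 43% | 68 / 69 / 71% | 61 / 69 / 82% |
| 80% vs 95% | 22 / 20 / 19% | 44 / 42 / 42% | 35 / 38 / 45% |
| 90% vs 97% | 5 / 5 / 5% | 16 / 15 / 13% | 10 / 10 / 11% |

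Full category rates assumed: 80% is (80, 12, 5, 3); 90% is (90, 7, 2, 1); 65% is (65, 20, 10, 5); 95% is (95, 3, 1, 1); 97% is (97, 2, 0.7, 0.3).

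The 2.8% at correlation 0 is not due to pairing. Sparse cells are the likely cause: at 80% first pass the expected counts per box are 30 × (0.80, 0.12, 0.05, 0.03) = 24, 3.6, 1.5 and 0.9. The pairing effect alone is the fall from 5.0% to 1.3% in the unpaired ordinal column.

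On power, most of the gain over chi-square comes from order. Comparing the last two columns, pairing costs 6 to 9 points at correlation 0, changes power by 0 to −5 points at 0.3, and at 0.6 adds 11 and 3 points in the first two power scenarios but loses about 2 in the third.

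**Step 3: separate check with other rates.** With three categories at 70/20/10% in both boxes (20,000 trials), chi-square rejects in 3.2% of trials at correlation 0.3, falling to 0.3% at 0.9. A paired marginal homogeneity test stays between 4.2% and 5.1% over correlations 0 to 0.9. At 50/30/20% versus 80/15/5%, power at correlations 0.3, 0.5, 0.7 and 0.9 is 63, 63, 63 and 66% for chi-square against 81, 88, 95 and 99.6% for the paired test.

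**Step 4: two examples by hand.** McNemar's statistic is (b − c)²/(b + c), where b and c are the two discordant counts.

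- First-pass success 22/30 versus 28/30. Expected counts are 25 and 5 per box, so chi-square = 2 × 9/25 + 2 × 9/5 = 4.32, p = 0.038, whatever the pairing. With discordant pairs 6 vs 0, 7 vs 1 or 8 vs 2, McNemar gives 36/6 = 6.0 (p = 0.014), 36/8 = 4.5 (p = 0.034) or 36/10 = 3.6 (p = 0.058).
- First-pass success 23/30 versus 16/30, with 15 people succeeding in both and discordant pairs 8 vs 1. Expected counts are 19.5 and 10.5, so chi-square = 2 × 12.25/19.5 + 2 × 12.25/10.5 = 3.59, p = 0.058. McNemar gives 49/9 = 5.44, p = 0.020 (exact p = 0.039).

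**The case against.** **Chi-square could mean McNemar.** McNemar's statistic is referred to a chi-square distribution. But it is not named, its usual form handles only yes/no data, and the plan's own example has more than two ordered categories. The same paragraph names the Mann-Whitney test, which also assumes separate groups, for intubation time. If a paired test was meant, the text still has to say so.

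**The error is safe and the endpoint minor.** This stands. Under positive correlation the test is conservative, no false claim in favour of either box follows, and the point is a companion to the same pairing error in the primary analysis.

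**The paired tests do not hold exactly 5% either.** True when data are sparse. Signed-rank is at 2.8 to 3.6% with 90% first pass, and mid-p McNemar at 3.2 to 4.1% with 80%. They remain closer to nominal than chi-square once there is correlation.

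**The case for pairing is weaker on power than it sounds.** Also true. Participants need more than 5 years' experience, so high first-pass rates are plausible, and at 90% versus 97% no test is useful. For a yes/no outcome at 80% versus 95%, mid-p McNemar has power 37 / 39 / 43% against 46 / 45 / 43% for chi-square. In the 22/30 versus 28/30 example, the only split that crosses 0.05 is 8 vs 2, where nobody fails in both boxes, which is negative association. The 23/30 versus 16/30 example shows a changed decision under positive association.

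None of this makes the planned test right for paired data.

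**Conclusion.** The concern holds. As written, the plan applies a test for separate groups to paired, ordered data, and its p-value does not have its stated 5% level if a person's two results are positively correlated. Under the assumed rates, chi-square on attempts rejects in roughly 1 to 2% of trials with no true difference at latent correlations 0.3 to 0.6 with four categories, and in 3.2% at 0.3 with three. Against a paired ordinal test it loses about 18 to 39 points of power at those correlations when the difference between boxes is large, and little of practical value when both boxes are near ceiling. The direction and the mismatch follow from the design; the sizes rest on assumed rates, assumed correlations and all 30 participants completing.

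The 4-point agreement items and the Cormack-Lehane grade are affected only if they are analysed as categorical, since the plan assigns neither by name to a test. This should be corrected, but it does not threaten the trial's main conclusion.

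**What to change.** In the Sample size section, replace the chi-square sentence with the following, applied to direct laryngoscopy and videolaryngoscopy separately:

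1. Number of attempts: a paired ordinal test (Wilcoxon signed-rank or marginal homogeneity). Use the same for the 4-point items and the Cormack-Lehane grade if they are treated as categorical.
2. Yes/no outcomes such as failed insertion: the asymptotic or mid-p McNemar test, with the paired difference in proportions and its 95% confidence interval. The reason is validity, not a general gain in power.
3. State how failures enter the attempts analysis. Failure also covers procedures over 120 seconds, so if failures are ranked as the worst category, one slow attempt ranks below three quick ones. The alternative is to analyse attempts as counted and report failure as a separate paired yes/no outcome.

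The cost is a change of wording and one stated choice; both boxes are already recorded on one sheet. The downside is that pairs with no difference carry no information. At 80% first pass and correlation 0, the expected number of differing pairs is 30 × (1 − 0.80² − 0.12² − 0.05² − 0.03²) = 10.3, so about 20 of 30 pairs drop out and some power can be lost if correlation is near zero.

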### **FLOW CHART**

# GANTT CHART OF RESEARCH ACTIVITIES PROJECT TITLE: TAIWAN "AEROSOL BOX" VERSUS UMMC "INTUBATION BOX": CLINICAL EVALUATION OF THE "INTUBATION BOX" FOR EASE OF INTUBATION

									YEA	R 2020								
	Apr	Apr	May	May	June	June	Jul		Aug	Aug	Sept			Oct	Nov	Nov	Dec	Dec
	1-15	16-30	1-15	16-31	1-15	16-30	1-15	16-31	1-15	16-31	1-15	16-30	1-15	16-31	1-15	16-30	1-15	16-30
ACTIVITIES																		
Submission for ethics																		
committee approval																		
Preparation of resources																		
required																	1	
Data collection																		
Data entry																		
Data analysis																		
Writing of report																		
Submission of completed paper to																		
ISI journal																		

# MILESTONES AND DATES CHART PROJECT TITLE: TAIWAN "AEROSOL BOX" VERSUS UMMC "INTUBATION BOX": CLINICAL EVALUATION OF THE "INTUBATION BOX" FOR EASE OF INTUBATION

									YEA	R 202	0							
	Apr	Apr	Ma	May	June	June	Jul	Jul	Aug		Sept	Sept	Oct	Oct	Nov	Nov	Dec	Dec
	1-	16-	у	16-	1-15	16-	1-	16-	1-	16-	1-	16-	1-	16-	1-	16-	1-	16-30
	15	30	1- 15	31		30	15	31	15	31	15	30	15	31	15	30	15	
ACTIVITIES			13															
Submission for ethics committee approval																		
Preparation of resources required																		
Data collection																		
Data entry																		
Data analysis																		
Writing of report																		
Submission of completed paper to ISI journal																		

Part 1: User profile			
Name:			
Professional category:	:		
Anaesthesia experienc	ce:		
Age:			
Gender:			
Part 2: Intubating co	onditions pr	ofile	
For direct laryngoscop	-		
		T-: D	HMMC D
Findings Time for successful		Taiwan Box	UMMC Box
(seconds)	IIIIuoaiioii		
Number of intubatio	n attempts		
POGO grading (%)			
Cormack Lehane gra	ade (1-4)		
For videolaryngoscop	y:		
Findings		Taiwan Box	UMMC Box
Time for successful		Turwun Don	CHAIC BOX
(seconds)			
Number of intubation	n attempts		
POGO grading (%)			
Cormack Lehane gra	ide (1-4)		
Part 3: Usability pro	file		
In this section, we wo		now the usability of this eq	uipment (Taiwan Box vs UMMC Box)
during intubation.			
When using for intul	hation with	direct laryngoscopy:	
Findings	vativn With	Taiwan Box	UMMC Box
On a scale of 0-			
10, how easy was	0	10	0

**Data collection sheet** 

Findings		Taiwa	n Box		UMMC Box					
On a scale of 0-10, how easy was it to use this box?	0 — Very o	difficult	Very	→ 10 y easy	0 — Very o	difficult	Very easy			
Please choose your level of			]	Degree of	agreement	:				
agreement with the statements below.	1: Strongly disagree	2: Disagree	3: Agree	4: Strongly agree	1: Strongly disagree	2: Disagree	3: Agree	4: Strongly agree		
It is comfortable for me to use										

this equipment				
My visual field is				
clear while using				
this equipment				
My hand				
movements were				
free while using				
this equipment				

[figure not shown]
When using for intubation with videolaryngoscopy:

Findings	Intubutio		n Box	ору .	UMMC Box					
On a scale of 0-10, how easy was it to use this box?	0 — Very	difficult	Very easy		0 Very difficult		Very easy			
Please choose your level of										
agreement with the statements below.	1: Strongly disagree	2: Disagree	3: Agree	4: Strongly agree	1: Strongly disagree	2: Disagree	3: Agree	4: Strongly agree		
It is comfortable for me to use this equipment										
My visual field is clear while using this equipment										
My hand movements were free while using this equipment										

Which box would you prefer to use?
Do you have any suggestions on how we can improve this equipment?

### APPENDIX A

### "PERCENTAGE OF GLOTTIC OPENING" VIEW (POGO)

The percentage of glottic opening (POGO) score for laryngeal grading. The POGO score represents the linear span from the anterior commissure to the interarytenoid notch. (source: "Laryngeal Exposure (Opening) Scores" https://www.e4ent.com/articles/laryngeal-exposure-opening-scores/)

### APPENDIX B
